2.2 Mutational landscape in pancreatic cancer

Next generation sequencing technologies have been used to characterize the mutational landscape in pancreatic cancer. Exome sequencing studies have revealed an average of 63 genetic alterations affecting 12 core cellular pathways [5]. The majority of these alterations were point mutations with the most frequently mutated genes being KRAS, TP53, and SMAD4. Tumors demonstrated heterogeneity in regard to the genomic alterations present, indicating that a spectrum of mutations are present across individual patients.

2.3 Tumor microenvironment

Pancreatic cancer has a robust desmoplastic stroma with an abundant leukocyte infiltrate [6, 7]. This stroma is implicated in resistance to conventional therapies by limiting effective delivery of therapies to malignant cells [8]. The immune infiltrate is predominantly tumor promoting cells derived from the bone marrow, including tumor associated macrophages and myeloid derived suppressor cells (MDSC) [9, 10]. Furthermore, effector tumor infiltrating lymphocytes are scarce with the majority of tumor infiltrating lymphocytes being immunosuppressive FoxP3⁺ regulatory T-cells (Tregs).

2.4 Tumor antigens

Tumor antigens are often classified as shared tumor antigens and tumor-specific antigens (neoantigens). The majority of tumor-specific antigens are now believed to be the result of somatic mutations present in the tumor.

Shared tumor antigens are expressed in multiple cancers, and are often self-differentiation antigens that are expressed in a limited subset of normal tissues, but overexpressed in cancers. Examples of shared tumor antigens include MAGE (melanoma) [11], prostatic acid phosphatase (prostate cancer) [12], and HER2/neu (breast cancer) [13]. Mesothelin is a shared tumor antigen that is highly expressed in pancreatic adenocarcinoma [14]. A listeria modified to express mesothelin has been used in pancreatic cancer clinical trials and has demonstrated safety and efficacy [15]. Jaffee et al. have characterized the immunogenic epitopes for mesothelin for the HLA-A1, HLA-A2, HLA-A3, and HLA-A24 alleles [16, 17].

Tumor-specific antigens (or neoantigens) are uniquely expressed in individual cancers, and are typically the result of point mutations or other genetic changes that are present only in the tumor (reviewed in [18, 19]). As such, tumor-specific antigens represent the only antigens that are truly unique to the tumor and not expressed in normal tissues. The first human mutant tumor-specific antigen was described in 1995, resulting from a point mutation of cyclin-dependent kinase (CDK4) [20]. Since that time additional publications have described the expression of neoantigens in melanoma [21], non-small cell lung cancer [22] and other human cancers [23].

Cancer vaccine strategies targeting neoantigens have substantial theoretical advantages over strategies targeting shared tumor antigens. Theoretical advantages include: (1) Targeting neoantigens is potentially safer. Neoantigens are expressed only in the tumor, decreasing the risk of autoimmunity. (2) Targeting neoantigens is potentially more effective. T cell responses to neoantigens are high in affinity and are not limited by central mechanisms of self-tolerance. (3) Targeting neoantigens potentially limits antigen-loss, a common tumor escape mechanism. One of the hallmarks of cancer is genome instability, and one clear weakness of cancer vaccines that target a single shared tumor antigen is antigen-loss. Targeting multiple neoantigens may preclude antigen loss. In addition, many neoantigens play a functional role in neoplastic transformation (driver mutations). (4) Targeting neoantigens is likely to be universally applicable in epithelial cancers, including pancreatic cancer. Epithelial cancers appear to have significant numbers of

nonsynonymous mutations present, suggesting that a personalized vaccine approach could be used in most patients with pancreatic cancer, regardless of HLA type.

We have recently used next generation sequencing technologies to identify and study neoantigens in more detail as described in the sections below [24, 25].

2.5 Next generation sequencing

Robust next-generation sequencing strategies for the identification of neoantigens will be required for the successful clinical translation of personalized cancer vaccine strategies. As such, a major focus of our research studies has been the development of cost-effective and accurate next-generation sequencing strategies to identify neoantigens and validate the expression of these antigens at the mRNA level. Initially a cancer genome sequencing approach was used. While cancer whole genome sequencing is informative and provides comprehensive information about both the coding and noncoding regions of the genome, this level of information may not be necessary for identifying neoantigens, or prioritizing antigens for immune intervention. We have now confirmed that tumor/normal exome sequencing is a robust and accurate strategy for the identification of neoantigens [24, 25]. Of note, recent studies suggest that approximately 40% of mutations identified by cancer exome sequencing are not expressed at the mRNA level, so it is important to confirm expression of the mutant allele at the mRNA level. To evaluate mRNA expression, we have performed cDNA-capture sequencing analyses. We have confirmed that cDNA-capture sequencing can be used to successfully confirm expression of sequencing-identified neoantigens at the mRNA level. This analysis also provides an estimation of how highly expressed the mutated allele is expressed relative to other genes in the tumor. For the phase 1 clinical trial proposed, tumor/normal exome sequencing analysis will be used to identify mutations (single nucleotide variants, insertions and deletions) present only in the tumor, and cDNA-capture sequencing will be used to confirm mutant allele expression and expression level in the tumor mRNA.

2.6 Personalized cancer vaccines

There are two conceptual strategies for creating personalized cancer vaccines targeting neoantigens: a candidate epitope strategy, and an unbiased strategy. The candidate epitope strategy uses computer algorithms [26, 27] and *in vitro* studies to predict immunodominant epitopes, which are then integrated into a personalized vaccine. In the unbiased strategy, no attempt is made to identify the immunodominant epitopes, and all candidate neoantigens are integrated into a personalized vaccine.

We have considered both the candidate epitope strategy and the unbiased strategy. We believe that the candidate epitope strategy is superior to the unbiased strategy for the following reasons. (1) Preliminary data from preclinical models and human correlative studies suggest that relatively few sequencing-identified neoantigens are processed, presented and effectively recognized by the immune system. (2) We have now developed and validated algorithms for the prediction and prioritization of sequencing-identified neoantigens [24, 25]. (3) Targeting a limited number of prioritized sequencing-identified neoantigens will facilitate vaccine design and manufacture and streamline immune monitoring.

2.7 Prioritization of sequencing-identified neoantigens

Of note, we have now developed and validated an epitope prediction algorithm for the prioritization of sequencing-identified neoantigens. Once somatic mutations have been identified and mutant mRNA expression confirmed/quantified using the sequencing strategies outlined above, neoantigens will be prioritized using an epitope prediction algorithm that has been designed to select and prioritize the most promising sequencing-identified neoantigens. Currently, the most commonly used CD8 T cell epitope prediction algorithm is NetMHC. However, collaborative work conducted by [name], [name], [name] and [name] has shown that a much more accurate prediction comes from calculating a median affinity for each sequencing-predicted mutant epitope using multiple available epitope prediction algorithms (i.e. NetMHC Pan; ANN; and SMM). We have significantly improved this epitope prediction algorithm by applying these filters to the initial prioritized output list: (a) elimination of hypothetical proteins; (b) use of an antigen processing algorithm to eliminate epitopes that are not likely to be proteolytically produced by constitutive proteasomes or immunoproteasomes; and (c) prioritization of “neo-epitopes” identified by a higher affinity binding of the mutant peptide sequence compared to the wildtype peptide sequence. The final output of these analyses is a rank-ordered list of the highest to

lowest priority sequencing-identified neoantigens for each individual patient. In experiments performed using preclinical mouse sarcoma models, this refined prediction algorithm has successfully identified the major tumor rejection antigens in three out of three tumors tested to date [24, 25]. To our knowledge, this is the only algorithm that has been successfully applied to date to cancer vaccine development. Additional information about the preclinical validation of the epitope prediction algorithm is provided in Section 5.2 Nonclinical Studies. MHC class II epitopes can also be accurately predicted using a similar algorithm ([name], unpublished data).

Once a rank-ordered list of the highest to lowest priority sequencing-identified mutant tumor-specific peptide antigens is generated, we will generate tetramers corresponding to the top 5-10 class I neoantigens using a photo-activated peptide tetramer protocol. We will stain T cells from the peripheral blood of subjects using a state-of-the-art CyTOF processor. Mutant epitopes associated with positive tetramer staining will be prioritized for the generation of neoantigen peptide vaccines. Once the candidate mutant epitopes have been verified, multivalent peptide vaccine construction will commence.

2.8 Synthetic long peptide vaccines

The neoantigen peptide vaccine strategy is based on the synthetic long peptide vaccine platform. We have focused on this platform because of the established safety and documented efficacy of this platform. First generation peptide-based cancer vaccines have typically included "minimal epitope" peptides, i.e. peptides of 9-10 amino acids in length known to bind to specific MHC class I alleles. First generation peptide-based cancer vaccines have an excellent safety profile and have been successful in inducing peptide-specific T cell responses in the peripheral blood of cancer patients, as measured by ELISPOT or tetramer analysis.

These initially promising results with first-generation peptide-based cancer vaccines prompted investigators to explore improvements to the platform. These investigations have resulted in "next-generation" peptide-based cancer vaccines [28] including synthetic long peptide vaccines. Synthetic long peptide vaccines are 25-30 amino acids in length and are processed by the immune system differently than minimal epitope peptide vaccines. This prolongs the duration of peptide presentation and T cell activation [29, 30]. Synthetic long peptide vaccines have proven to be both safe and remarkably effective in clinical translation [31]. In our previous experience, we have been able to successfully design and manufacture neoantigen synthetic long peptide vaccines in > 85% of cases. Processing of synthetic long peptides and T cell activation can be further enhanced through the activation of toll-like receptors on the surface of APC. In particular, the TLR3 agonist, poly-ICLC is commonly used as an adjuvant to enhance the efficacy of peptide-based cancer vaccines, including synthetic long peptide-based vaccines [31].

2.9 Clinical trial design and dose considerations

The early clinical development paradigm for chemotherapeutic agents has significantly influenced the development of therapeutic cancer vaccines. However, there are major differences between these two classes of therapeutics that have important implications for early clinical development. Specifically, the phase 1 concept of dose escalation to find a maximum-tolerated dose does not apply to most therapeutic cancer vaccines. Most therapeutic cancer vaccines are associated with minimal toxicity at a range that is feasible to manufacture or administer, and there is little reason to believe that the maximum-tolerated dose is the most effective dose.

In a recent article from the biostatistics literature, Simon et al. write that "the initial clinical trial of many new vaccines will not be a toxicity or dose-ranging trial but rather will involve administration of a fixed dose of vaccine ... in most cases the dose selected will be based on preclinical findings or practical considerations. Using several dose levels in the initial study to find the minimal active dose or to characterize the dose-activity relationship is generally not realistic" [32].

The peptide vaccine will integrate multiple peptides corresponding to prioritized neoantigens in combination with the molecular adjuvant poly IC:LC. We propose to test a fixed dose of peptide consistent with recent reports [33]. The final peptide concentration is 300 µg/mL of each peptide after mixture with poly-ICLC

2.10 Challenges of sequencing pancreatic cancers

The challenges of performing massively parallel sequencing (MPS) assays from clinical pancreatic cancer samples are considerable. At its essence, pancreatic adenocarcinoma has a low cellularity, with many stromal cells interspersed with the pancreatic cancer cells. A pathologist who is a specialist in gastrointestinal cancers will survey the tumor to identify islands of high tumor cellularity and take 1mm punches from formalin fixed paraffin embedded (FFPE) tissues. By selecting these areas for sequencing we are able to enrich the tumor purity to the level that allows neoantigen identification. Additionally, since the tissues have been previously subjected to FFPE, some degradation of the nucleic acids may result, further complicating the sample quality toward MPS.

Nevertheless, our group has worked extensively to optimize MPS library construction techniques that enable high diversity libraries to be constructed from as little as 10 ng of input DNA. In particular, we currently utilize the Swift Biosciences Accel-NGS 2S kit that is optimized for low input DNA from FFPE samples with an input range of 10-50 ng of isolated DNA. The resulting libraries have proven suitable for subsequent exome capture by hybridization such as the Integrated DNA Technologies (IDT) Rapid Exome reagent. This commercially available reagent has superior performance on FFPE-derived DNA libraries, and has a rapid hybridization time of only 4 hours, permitting a one-day turn around for library construction, quantitation, and hybrid capture prior to sequencing.

Another challenge of pancreatic adenocarcinoma is the rapid degradation of RNA that often occurs during surgery. Our surgical team has been evaluating whether the RNA stability can be influenced by changes to the surgical procedure that reduce ischemia time during surgery. In our early experience with several samples, this alteration in the surgical procedure leads to dramatic improvements to the RNA stability as gauged by RNA integrity (RIN) values obtained from our post-isolation QC procedures. In turn, the MPS libraries generated from these pancreatic RNAs are of high quality and diversity.

3 PATIENT SELECTION

3.1 Inclusion criteria

A patient will be eligible for evaluation and sequencing of tissue for vaccine development (Step 0) and vaccine administration (Step 1) only if ALL of the following criteria apply:

1. Histologically or cytologically confirmed diagnosis of pancreatic adenocarcinoma; mixed histology will be included as long as the predominant histology is adenocarcinoma.
2. Completed an R0 or R1 surgical resection as determined by pathology
3. Pathology review demonstrates tumor cellularity no less than 30% in quantities sufficient to obtain 6-8 1mm biopsies from the original FFPE blocks.
4. At least 18 years of age.
5. Life expectancy of > 12 months.
6. ECOG performance status ≤ 2
7. Normal bone marrow and organ function as defined below:
 - a. WBC $\geq 3,000/\mu\text{L}$
 - b. absolute neutrophil count $\geq 1,500/\mu\text{L}$
 - c. platelets $\geq 100,000/\mu\text{L}$
 - d. total bilirubin $\leq 1.5 \times$ institutional upper limit of normal
(Subjects with Gilbert's syndrome may be enrolled despite a total bilirubin level $>1.5 \text{ mg/dL}$ if their conjugated bilirubin is $<1.5 \times$ ULN)
 - e. AST/ALT $\leq 2.5 \times$ institutional upper limit of normal
 - f. creatinine $\leq 1.5 \times$ institutional upper limit of normal
8. International Normalized Ratio (INR) and activated partial thromboplastin time (PTT) $< 1.5 \times$ ULN provided the patient is not on anticoagulation therapy.
9. Patients who have had a stent placed for biliary obstruction can be included in the study provided serum bilirubin at time of enrollment is within protocol limits.
10. Women of child-bearing potential and men must agree to use adequate contraception (hormonal or barrier method of birth control, abstinence) prior to study entry and for the duration of study participation. Should a woman become pregnant or suspect she is pregnant while participating in this study, she must inform her treating physician immediately.
11. Able to understand and willing to sign an IRB approved written informed consent document.

3.2 Exclusion criteria

A patient will be ineligible for inclusion in this study if ANY of the following criteria apply:

1. Evidence of neuroendocrine tumor, duodenal adenocarcinoma, or ampullary adenocarcinoma.
2. Received neoadjuvant chemotherapy for their pancreatic adenocarcinoma.
3. Evidence of disease recurrence or metastasis following surgical resection at any time prior to the first vaccination administration. Most patients will undergo restaging midway through adjuvant chemotherapy and at the completion of therapy; however, timing of imaging is at the discretion of the patient's medical oncologist.
4. History of other malignancy ≤ 3 years previous with the exception of basal cell or squamous cell carcinoma of the skin which were treated with local resection only, carcinoma *in situ* of the cervix, or LCIS/DCIS of the breast.
5. Known allergy, or history of serious adverse reaction to vaccines or TLR agonists such as anaphylaxis, hives, or respiratory difficulty.

6. Acute or chronic, clinically significant hematologic, pulmonary, cardiovascular, hepatic renal, and/or other functional abnormality that would jeopardize the health and safety of the participant as determined by the investigator based on medical history, physical examination, laboratory values, and/or diagnostic studies.
7. A psychiatric illness/social situations that would limit compliance with study requirements as determined by the investigator from the medical history, physical exam, and/or medical record
8. Prior or currently active autoimmune disease requiring management with immunosuppression. This includes inflammatory bowel disease, ulcerative colitis, Crohn's disease, systemic vasculitis, scleroderma, psoriasis, multiple sclerosis, hemolytic anemia, immune-mediated thrombocytopenia, rheumatoid arthritis, systemic lupus erythematosus, Sjögren's syndrome, sarcoidosis, or other rheumatologic disease or any other medical condition or use of medication (e.g., corticosteroids) which might make it difficult for the patient to complete the full course of treatments or to generate an immune response to vaccines. In the case of asthma or chronic obstructive pulmonary disease taking inhaled corticosteroids that does not require daily systemic corticosteroids is acceptable. Additionally, local acting steroids (topical, inhaled, or intraarticular) will be allowed. Patients on intermittent or short course steroids will be allowed if the dose does not exceed 4 mg of dexamethasone (or equivalent) per day for > 7 consecutive days. Any patients receiving steroids should be discussed with the PI to determine if eligible.
9. Pregnant and/or breastfeeding.
10. Known HIV-positive status. These patients are ineligible because of the potential inability to generate an immune response to vaccines.

3.3 Step 1 eligibility

At Step 1 eligibility confirmation prior to vaccination, the above criteria must be met plus:

1. Completed adjuvant chemotherapy:
 - a. Initiation of adjuvant chemotherapy within 16 weeks of surgery
 - b. Completion of at least 4 months of adjuvant chemotherapy with gemcitabine/capecitabine FOLFIRINOX, or similar adjuvant chemotherapy at the discretion of the patient's medical oncologist.
 - c. Additional chemoradiation therapy as recommended by the patient's medical oncologist.
 - d. Reimaging post-completion of chemotherapy demonstrates no evidence of recurrent disease and CA 19-9 is less than 92.5 u/mL.
 - e. Dose modifications and/or delays in adjuvant chemotherapy is at the discretion of the treating physician
2. There is a 1 week washout prior to Day 1 of vaccine for patients on daily systemic steroids at doses exceeding 10 mg prednisone.
3. Receiving any other investigational agents, or has received an investigational agent within the last 30 days.

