4.2 Registration procedures

Patients must not start any protocol intervention prior to registration through the Siteman Cancer Center.

Registration for this trial will be a two-step process. Step 0 will be screening and confirmation of eligibility for vaccine creation. Step 1 will be screening and confirmation of eligibility for vaccine administration. See Section 3: Patient Selection for eligibility criteria for each step and Section 8: Study Calendar for screening procedures for each step.

Step 0 screening must occur within 16 weeks of surgical resection, and Step 0 enrollment can occur up to four weeks after initiation of adjuvant chemotherapy. Step 1 screening will occur when the patient's vaccine is ready or nearly ready, but must be within 14 days of the first vaccine administration.

The following steps must be taken before registering patients to this study:

- (1) Confirmation of patient eligibility by Washington University (applies to both Step 0 and Step 1)
- (2) Registration of patient in the Siteman Cancer Center database (This will be done by Washington University research coordinator. Step 0 enrollment will be "On Study" in the OnCore database, and Step 1 enrollment will be "On Treatment" in the OnCore database.)
- (3) Assignment of unique patient number (UPN)

Once the patient has been entered in the Siteman Cancer Center OnCore database, the WUSM coordinator will forward verification of enrollment and the UPN via email.

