4.3 Confirmation of patient eligibility

Confirm patient eligibility for both Step 0 and Step 1 by collecting the information listed below and scanning and emailing it to the research coordinator listed in the *Siteman Cancer Center Clinical Trials Core Protocol Procedures for Secondary Sites* packet at least two business days prior to registering patient (if a quicker turnaround is needed, please contact primary study coordinator at Washington University):

- (1) Your name and contact information (telephone number, fax number, and email address)
- (2) Your site PI's name, the registering MD's name, and your institution name
- (3) Patient's race, sex, and DOB
- (4) Three letters (or two letters and a dash) for the patient's initials
- (5) Currently approved protocol version date
- (6) Copy of signed consent form (patient name may be blacked out)
- (7) Planned date of enrollment
- (8) Completed eligibility checklist, signed and dated by a member of the study team
- (9) Copy of appropriate redacted source documentation confirming patient eligibility

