6.2 Concomitant Medication Guidelines

Patients may receive other vaccinations while on study, including influenza and pneumococcal.

Patients will be treated for toxicities at the discretion of the physician. Growth factor support with either filgrastim or pegfilgrastim is at the discretion of the investigator.

There are no prohibited medications.

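### Step 1 eligibility lists use of another investigational agent among the conditions to be met, so the protocol's only rule on the subject points the wrong way as written

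*Combined protocol and SAP*

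**What the plan says.** Section 3 sets eligibility in three parts. Section 3.1 lists inclusion criteria. Section 3.2 lists ten exclusions under the sentence "A patient will be ineligible for inclusion in this study if ANY of the following criteria apply". Section 3.3 adds conditions for vaccination and opens with "At Step 1 eligibility confirmation prior to vaccination, the above criteria must be met plus".

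Three numbered items follow in Section 3.3:

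1. "Completed adjuvant chemotherapy", with sub-items on timing, duration and re-imaging.
2. "There is a 1 week washout prior to Day 1 of vaccine for patients on daily systemic steroids", above a stated prednisone dose.
3. "Receiving any other investigational agents, or has received an investigational agent within the last 30 days".

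Section 4.2 sends the reader back for the criteria: "See Section 3: Patient Selection for eligibility criteria for each step". Section 4.3 requires, for each step, a "Completed eligibility checklist, signed and dated by a member of the study team", together with source documents that confirm eligibility. On concomitant treatment, Section 6.2 says "There are no prohibited medications".

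**The concern.** An item under a lead-in that demands conditions be met should describe something the patient must satisfy. Item 3 describes something that a trial would normally rule out. It has neither a negative nor an exclusion heading of its own, so the text asks for the opposite of what its phrasing suggests was intended.

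The direction of this rule matters more here than in a controlled trial. The study is open-label with a single arm. The primary safety assessment depends on judging whether events are related to vaccination, and under Section 12.2 a single Grade 3 or 4 event judged probably or definitely related halts injections and enrolment. The secondary objective compares antigen-specific T cells before and after vaccination in the same patients. With no control group, the protection against a recent second agent muddying either assessment is a clear eligibility rule, and item 3 is the only one the protocol has.

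There is also a compliance side. Section 15 makes screening and enrolment an audit item, and Section 20.4 defines a deviation by reference to the approved text. Sites should not have to depart from the approved wording in order to follow its evident purpose.

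**Working it through.** No arithmetic applies. The check is whether the text supports an exclusionary reading of item 3, either in its own place or from elsewhere.

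**Step 1: the lead-in and the items of Section 3.3.** The lead-in calls for the earlier criteria to be satisfied and then adds the numbered items. Item 1 is a positive requirement (chemotherapy completed). Item 2 is a positive requirement (a washout has taken place where it applies). Item 3 is grammatically parallel to these and has no negation. The numbering runs from 1 to 3 without a break, and nothing suggests a lost subheading between items 2 and 3.

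**Step 2: the two readings applied to two patients.**

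| Patient at Step 1 | Item 3 as a condition to be met (literal) | Item 3 as an exclusion (inferred) |
|---|---|---|
| No other investigational agent now or in the past 30 days | Fails | Passes |
| On another agent, or had one in the past 30 days | Passes | Fails |

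The readings disagree for every patient, so there is no group for whom the wording is harmless.

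**Step 3: a search for text that settles the direction.**

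- Section 3.1: silent on investigational agents.
- Section 3.2: none of the ten exclusions names them. Exclusion 8 reaches medication that might impair the immune response, which overlaps in part but is not the same rule.
- Section 4.2: defers to Section 3 and adds no rule of its own.
- Section 6.2: bars no medication, so it gives no support to the exclusionary reading. It also leaves open whether another agent could be started after Step 1.

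Nothing states the rule in the opposite direction. That item 3 is meant to exclude is an inference from its phrasing, and the documents never say so.

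**Step 4: whether the rule could simply move to Section 3.2.** Section 3.2 governs inclusion in the study as a whole, which starts at Step 0. Section 4.2 allows Step 0 enrolment up to four weeks after adjuvant chemotherapy begins. Section 3.3 requires at least 4 months of that chemotherapy before vaccination. So at least about three months (4 months less 4 weeks) separate the two points. A 30-day look-back placed in Section 3.2 would also apply at Step 0, which is a new restriction. Only rewording in place keeps the rule's timing.

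**Step 5: effect on the statistics.** The sample-size reasoning in Sections 13.1.1 to 13.1.3 does not use this rule. Nothing needs recomputing.

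**The case against.** The strongest reply is that nobody would apply item 3 literally. It uses familiar exclusion phrasing, and an experienced coordinator would read it that way. The lead-in is loose in any case. It also sweeps in the Section 3.2 exclusions as criteria to be met, and sub-items 1c and 1e (chemoradiation as recommended, dose changes at the physician's discretion) are not requirements either. Washington University confirms eligibility for both steps at both sites against source documents, which lowers the chance that the two sites read the item differently.

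Most of this stands, and it limits the consequences. It does not remove the fault. The looseness of the lead-in cannot turn item 3 into an exclusion, because the item comes after the word that adds new conditions and beside two genuine requirements. A central check also needs a rule to check against, and the written one is reversed.

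A reader might go further and infer that suitable patients would be turned away wholesale, that patients on other agents would be selected so that the safety and T-cell results are confounded, or that every vaccinated patient becomes a protocol deviation. Each needs sites to follow the literal wording, and nothing in the documents makes that likely. A reader might also infer that the eligibility checklist is wrong. The checklist is not among the documents, so whether it repeats the wording is unknown.

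**Conclusion.** Item 3 of Section 3.3 is wrong as written: its direction contradicts its lead-in, and no other section corrects it. It is an internal inconsistency in an operative eligibility rule and does not call any design decision into question. It should be corrected.

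Its reach is every Step 1 registration, which means 15 evaluable patients by Section 13.1.1 and the Summary's enrolment figure, or 20 by Section 13.1. That count is how many times the rule is applied and is not a forecast of patients affected. The expected practical effect is small if sites read the item as an exclusion, and no numerical result in the plan depends on it.

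The conclusion rests on one inference, that the item was meant to exclude. The sponsor should confirm it. If it were not so, the literal rule would bar patients with no other investigational exposure, which nothing else in the protocol supports.

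**What to change.** - Reword item 3 where it stands so that it reads as a condition to be met. For example: at Step 1 the patient is not taking another investigational agent and has had none in the preceding 30 days. The 30-day figure is unchanged.
- Keep it a Step 1 criterion. Do not move it to Section 3.2, since that would extend it to Step 0.
- Reconcile it with Section 6.2, so that the protocol says whether the statement on concomitant medication covers other investigational agents after Step 1. The content of that rule is for the sponsor to decide.
- Check the Step 1 eligibility checklist in use at both sites, and correct it only if it carries the same wording.

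The cost is a one-line amendment to Section 3.3, a clarifying phrase in Section 6.2 and a short document check. Sample size, visits and analyses are untouched.
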